Title: Treatment of Full-Thickness Wounds: NPWT Combined with Type-I Collagen Based Advanced Skin Substitute Versus NPWT Alone

NCT No: NCT06873867

Date: November 09, 2025

INTRODUCTION

Full-thickness wounds, which extend through the dermis into the underlying subcutaneous tissue or deeper structures, remain a formidable challenge in reconstructive and wound care practice. These wounds may arise from trauma, surgical dehiscence, pressure injuries, or chronic ulceration, and are often complicated by infection, vascular insufficiency, and comorbidities such as diabetes and peripheral vascular disease. They affect millions of patients worldwide and impose substantial economic burden on healthcare systems [1, 2]. They are a growing concern in healthcare due to their prolonged healing time, high recurrence, and associated morbidity [3, 4]. These wounds often demonstrate delayed healing and increased risk of complications including infection, chronic inflammation, and impaired tissue regeneration [5, 6]. Without optimal management, these wounds fail to heal through the conventional stages of wound repair, functional impairment, increased risk of limb loss, poor cosmetic results and high healthcare costs. The complex pathophysiology of wound healing involves intricate interactions between cellular components, growth factors, extracellular matrix proteins, and vascular elements, necessitating comprehensive therapeutic approaches to optimize clinical outcomes [7].

Negative Pressure Wound Therapy (NPWT) has emerged as an effective modality to accelerate wound healing by removing excess exudate, enhancing perfusion, promoting granulation tissue formation and maintains an optimal wound environment, and thus is a cornerstone in treatment of complex wounds [8, 9, 10]. By applying controlled sub-atmospheric pressure, NPWT reduces interstitial edema, increases local blood flow, removes exudate, and stimulates granulation tissue formation. The application of controlled negative pressure creates a conducive environment for cellular proliferation and angiogenesis, facilitating the wound healing cascade [11, 12]. Despite its advantages, NPWT alone may not suffice for extensive tissue regeneration and achieve rapid epithelialization, especially in large or complex wounds where the extracellular matrix (ECM) and vascular supply has been significantly compromised [13].

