The present study aims to compare the clinical outcomes of NPWT combined with HPTC skin substitute versus NPWT alone in patients with full-thickness wounds, using a randomized controlled design, to provide robust evidence for clinical decision-making in advanced wound care. Our hypothesis is that the combination therapy will result in significantly greater wound area reduction, faster closure, improved scar quality, and better patient-reported pain outcomes, without increasing adverse events.

MATERIALS AND METHODS

This was a prospective, randomized, open-label, parallel-group clinical trial conducted at the Department of Plastic, Reconstructive, and Aesthetic Surgery, Adichunchanagiri Institute of Medical Sciences (AIMS), Karnataka, India. The study compared the efficacy of Negative Pressure Wound Therapy (NPWT) combined with High Purity Type-I Collagen (HPTC) skin substitute versus NPWT alone in the management of full-thickness wounds. Patient recruitment occurred between March 2025, and July 2025. The anticipated follow-up continued until August 2025, with each participant observed for a total of seven weeks (six weeks of intervention plus one-week follow-up). The trial was registered prospectively with **ClinicalTrials.gov (ID: NCT06873867)** and approved by the Institutional Ethics Committee (**Approval No: AIMS/IEC/013/2025**). The study adhered to the principles of the Declaration of Helsinki and Good Clinical Practice guidelines. All participants provided written informed consent prior to enrollment after comprehensive explanation of study procedures, risks, and benefits. Patient confidentiality was maintained throughout the study period.

Patients aged 18-80 years with full-thickness wounds (wound depth extending through dermis into subcutaneous tissue), including traumatic, post-surgical dehiscence, burns ulcers, pressure ulcers, DFUs, or VLUs, wound size $>20 \text{ cm}^2$ and $<75 \text{ cm}^2$, with adequate vascular supply to the wound site, ability to comply with treatment protocol and follow-up visits, and provided written informed consent were eligible.

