All patients received standardized wound care including sharp debridement as needed to remove non-viable tissue, infection control with topical antimicrobials when indicated, pressure redistribution and offloading as appropriate, nutritional assessment and optimization, glycemic control for diabetic patients, compression therapy for venous ulcers and pressure offloading for wounds when appropriate. Patient education on wound care was given.

Outcome Measures

The primary outcome of the study was percentage wound area reduction from week 1 through week 6 plus 1 week follow up, measured via digital photography. Measurements were performed by trained personnel blinded to treatment allocation.

Secondary outcomes included time to complete wound closure (in days) within 7 weeks, proportion of patients achieving complete closure by week 7, histological vascularity infiltration, between baseline (Day 0) and Day 5 biopsies, mean number of applications of the skin substitute required, incidence of adverse events (infection, allergic reaction, bleeding,

maceration), pain score change using a 0–10 Visual Analog Scale (VAS) from baseline to week 6, and scar quality assessed at week 7 using the Manchester Scar Scale (MSS).

Complete wound closure is defined as 100% epithelialization. Histopathological assessment included taking punch biopsies (2 mm) from the wound edge at baseline and day 5 post-intervention under local anesthesia (2% lidocaine without epinephrine). Fixation in 10% neutral buffered formalin for 24 hours, processing through graded alcohol and paraffin embedding, and serial sectioning at 4 μ m thickness was done. Samples were processed using standard histological techniques and stained with hematoxylin and eosin (H&E), Masson's trichrome, CD31 immunohistochemistry, and α -SMA immunohistochemistry. Assessment parameters included vascular infiltration (0-3 scale), neo-epithelialization (0-3 scale), fibroblast activity (0-3 scale), capillary density (vessels per mm²), inflammatory response (0-3 scale) and collagen deposition (0-3 scale) (Table 1).

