		Very high activity with extensive matrix deposition	3
Capillary density	Evaluated using CD31 staining, counted as vessels per mm^2 of tissue		
Inflammatory response	Graded semi-quantitatively (0–3 scale)	Minimal inflammatory infiltrate	0
		Mild chronic inflammation	1
		Moderate mixed inflammation	2
		Severe acute inflammation	3
Collagen deposition	Assessed using Masson's trichrome staining (0–3 scale)	Minimal collagen matrix	0
		Loose, immature collagen	1
		Moderate organized collagen	2
		Dense, mature collagen architecture	3

Table 2: Vancouver Scar Scale

Parameter	Score
Vascularity	0–3
Normal	0
Pink	1
Red	2
Purple	3
Pigmentation	0–2
Normal (matches surrounding skin)	0
Hypopigmentation	1
Hyperpigmentation	2
Pliability	0–5
Normal	0
Supple (flexible with minimal resistance)	1
Yielding (gives way to pressure)	2
Firm (resists movement)	3
Banding / rope-like tissue (may blanch on extension)	4
Contracture (permanent shortening producing deformity)	5
Height / Thickness	0–3
Flat / normal	0
< 2 mm	1
2–5 mm	2
> 5 mm	3

Parameter	Score
Total Scar Score (Higher scores indicate greater scar severity)	0-13

Data Collection and Measurement

Wound photographs were obtained using standardized digital photography with measurement grids. Standardized wound assessments were performed including digital photography, wound measurements using validated techniques, and clinical evaluations. Wound area was calculated by tracing the wound margin onto a sterile transparent film and photographing with a scale reference. Histological evaluation was performed on wound biopsies with stains as mentioned in Table 1. Pain assessments (Visual Analogue Scale) and quality of life score were completed at baseline, every week thereafter for 7 weeks.

Statistical Analysis

All data were analyzed using SPSS version 26.0 (IBM Corporation, Armonk, NY). Continuous variables were expressed as mean \pm standard deviation and compared using independent t-tests or Mann–Whitney U tests where appropriate. Categorical variables were expressed as frequencies and percentages, compared using chi-square or Fisher’s exact test. Repeated measures ANOVA was employed for longitudinal outcome analysis. Time-to-event outcomes were analyzed using Kaplan-Meier survival analysis with log-rank tests.

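### Complete closure has no durability requirement, so a wound that closes and reopens within seven weeks can count as closed, and no planned closure or safety outcome reports the reopening

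*Combined protocol and SAP*

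**What the plan says.** All references are to the combined protocol and SAP.

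- **Outcome Measures, definition:** "Complete wound closure is defined as 100% epithelialization". No confirming assessment, minimum duration or rule for a reopened wound is attached to it there or elsewhere.
- **Outcome Measures, secondary outcomes:** the two closure endpoints are "time to complete wound closure (in days) within 7 weeks, proportion of patients achieving complete closure by week 7".
- **Statistical Analysis:** for the first, "Time-to-event outcomes were analyzed using Kaplan-Meier survival analysis with log-rank tests". For the second, the general rule applies: "Categorical variables were expressed as frequencies and percentages, compared using chi-square or Fisher’s exact test".
- **Outcome Measures, adverse events:** infection, allergic reaction, bleeding and maceration are named. Reopening or recurrence is not.
- **Materials and Methods:** each participant is observed for seven weeks, described as "six weeks of intervention plus one-week follow-up".
- **Outcome Measures, primary outcome:** percentage wound area reduction from week 1 through week 6 and the follow-up week.
- **Introduction:** full-thickness wounds are described as having "prolonged healing time, high recurrence, and associated morbidity".

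**The concern.** Faster closure is one of the trial's stated hypotheses, and the closure endpoints are what a clinical reader will look at for it. Epithelialization can be complete at one visit and broken at a later one. The enrolled wounds include pressure ulcers, diabetic foot ulcers, venous leg ulcers and surgical dehiscence. If transient closure is scored the same as closure that holds to the end of observation, the reported closure rates are too high as a description of wounds that are closed. The report would also give the reader no way to see this, because reopening is not planned to be reported in any closure or safety outcome. The follow-up week after the intervention period offers a natural check that closure held, but neither closure endpoint is written to use it.

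**Working it through.** **1. How the text treats a reopened wound.** Take a wound fully epithelialized at week 4 and open at week 6.

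- *Time to closure.* The endpoint is "time to complete wound closure (in days) within 7 weeks", analysed by Kaplan-Meier. The event is reached at the first assessment showing 100% epithelialization, after which the patient leaves the risk set. Nothing in Statistical Analysis reverses the event. The wound is an event at week 4.
- *Proportion closed.* Achieving closure *by* week 7 is most naturally met once closure has been seen at any time up to week 7. The wound is a success. Status *at* week 7 is a possible reading, under which it is a failure, but the text does not say so.
- *Safety.* Reopening is not among the named adverse events.
- *Primary outcome.* The wound has a positive area at week 7, so its area reduction there is below 100%. This is the one planned outcome that would reflect it, though not labelled as a reopening.

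**2. Size under equal reopening.** The plan gives no closure or reopening rate, so there is no figure of its own to reproduce, and all rates below are assumptions. With ever-closed proportion p and reopened share r, the proportion closed at week 7 is p × (1 − r). Assume p = 70% and 50%, a 20-point difference on first closure.

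| r, both arms | Closed at week 7 | Difference |
|---|---|---|
| 5% | 66.5% vs 47.5% | 19 points |
| 10% | 63% vs 45% | 18 points |
| 20% | 56% vs 40% | 16 points |

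At r = 10% and the planned 52 per group, 52 × 0.70 × 0.10 = 3.6 and 52 × 0.50 × 0.10 = 2.6 patients would be counted as closed while open.

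**3. Does earlier closure by itself tilt the comparison?** Earlier closures have more time in which to reopen. Assume a constant weekly closure probability that reaches 70% and 50% by week 7, and one weekly reopening risk common to both arms.

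- Weekly closure probability: 1 − 0.30^(1/7) = 15.8% and 1 − 0.50^(1/7) = 9.4%.
- Mean weeks from closure to week 7 among closed wounds: 3.67 and 3.39, a ratio of about 1.08.
- At a 3% weekly risk, 10.4% and 9.7% of closed wounds reopen. Closed at week 7: 62.7% vs 45.2%, a difference of 17.5 points.
- At 2% and 5% weekly, the differences are 18.3 and 16.0 points.

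Most of the fall from 20 points comes from both rates dropping. The timing effect adds little.

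**4. If reopening differs by arm (assumed either way).** With 15% vs 5%: 0.70 × 0.85 − 0.50 × 0.95 = 59.5% − 47.5% = 12 points. With 5% vs 15%: 0.70 × 0.95 − 0.50 × 0.85 = 66.5% − 42.5% = 24 points. The difference can shrink or widen, and the documents support neither split.

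**5. Closures that cannot be confirmed.** At a constant weekly closure rate, with S7 the proportion still open at week 7 and S6 = S7^(6/7), the share of closures first seen at week 7 is (S6 − S7) / (1 − S7).

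- Total closure 40%: (0.645 − 0.600) / 0.400 = 11.4%
- Total closure 60%: (0.456 − 0.400) / 0.600 = 9.3%
- Total closure 80%: (0.252 − 0.200) / 0.800 = 6.5%

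**The case against.** The strongest reply is that the documents nowhere state a single-sighting rule. It is inferred from silence, and the proportion could have been scored as status at week 7. That stands as a limit on the point. It does not remove it, because the week 7 status reading is unwritten and the time-to-closure endpoint would still take the first closure.

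Second, both endpoints are secondary, the sample size rests on area reduction, and the primary outcome would pick up a wound open at week 7. This also stands, and it limits how much is at stake.

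Third, a reader might infer that the rule favours the combination arm because it is hypothesised to close wounds sooner, or take the 12-point figure in step 4 as the likely size. The documents support neither. With a common weekly reopening risk the timing effect is slight, the 12-point case needs a threefold difference in reopening between arms for which there is no basis, and the reverse split widens the difference instead.

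Fourth, a reader might treat the Introduction's mention of high recurrence as evidence of frequent reopening inside seven weeks. It is general background without a time frame or a rate.

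Fifth, confirmation at the next weekly visit alone would not be enough. A wound closed at weeks 4 and 5 and open at week 6 would still count as an event.

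**Conclusion.** The point holds as a gap in the endpoint definition. Closure carries no requirement that it last. On the natural reading a reopened wound is an event in the time analysis and a success in the proportion, and no planned closure or safety outcome shows it. The effect on the between-arm comparison cannot be sized from the documents, and its direction is unknown. Under an assumed 10% reopening in both arms, a 70% versus 50% difference becomes 18 points instead of 20, a modest change. The primary outcome is not affected by the closure definition.

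**What to change.** - Define the proportion endpoint as wounds 100% epithelialized at the week 7 assessment.
- Keep time to first closure. Add a sensitivity analysis that counts a closure as an event, dated to its first sighting, only if the wound is still closed at every later assessment through week 7.
- Show closures first seen at week 7 separately as unconfirmed.
- Report reopenings by arm.
- State which rule was actually applied. The document is dated November 2025 and anticipated follow-up to end in August 2025, so any analysis that departs from the applied rule should be labelled post hoc.

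No new patients or visits are needed, because wound area is already followed through the follow-up week. The explicit weekly schedule in Data Collection and Measurement covers pain and quality of life. Weekly wound images are implied by the primary outcome, so their availability should be checked first. The cost is slightly lower closure rates, and about 7% to 11% of closures (at an assumed constant weekly rate) would be first seen at week 7 and have no confirming visit.

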Quality of Life Assessment using EQ-5D-5L (EuroQol 5-Dimension 5-Level) [25] questionnaire, a standardized and widely used instrument for assessing health-related quality of life (HRQoL). Developed by the EuroQol Group [25], it provides a simple, generic measure applicable to a wide range of diseases and health conditions. The tool evaluates five key dimensions of health - mobility, self-care, usual activities, pain/discomfort and anxiety/depression. Each dimension is rated on five levels of severity - no problems, slight problems, moderate problems, severe problems and extreme problems or inability. These combinations describe a respondent's health state, which can be converted into a single summary index score (ranging from less than 0, indicating health states worse than death, to 1.0, representing full health) using country-specific value sets derived from general population preferences. In addition, the EQ-5D-5L [25] includes a Visual Analogue Scale (EQ-VAS) [25], a 0-100 scale on which patients rate their overall health (0 = worst imaginable health, 100 = best imaginable health). The EQ-5D-5L questionnaire was used in its validated Kannada Version 1.1 format, obtained directly from the EuroQol Group under non-commercial registration (ID: 78665). The tool was administered in interviewer-assisted digital format to ensure accurate comprehension by all participants.

Scar quality was assessed using Vancouver Scar Scale evaluating vascularity, pigmentation, pliability and height/thickness with total score ranging from 0 to 13 (lesser the score better the scar) (Table 2).

Table 1: Histological parameters evaluated in the ulcer bed at baseline and on day five of application

Parameter	Measurement tool	Criteria	Score
Vascular infiltration	Assessed by counting new blood vessels (0–3 scale)	Minimal vascular ingrowth (<5 vessels/HPF)	0
		Mild infiltration (5–10 vessels/HPF)	1
		Moderate infiltration (11–20 vessels/HPF)	2
		Abundant infiltration (>20 vessels/HPF)	3
Neo-epithelialization	Measured as epithelial migration distance from wound edge (0–3 scale)	No epithelial migration	0
		Minimal migration (<25% wound coverage)	1
		Moderate migration (25–75% coverage)	2
		Extensive migration (>75% coverage)	3
Fibroblast activity	Quantified by counting α -SMA positive fibroblasts per HPF and assessment of fibroblast morphology (0–3 scale)	Sparse, inactive fibroblasts	0
		Moderate cellularity, minimal matrix production	1
		High cellularity, active-matrix synthesis	2

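### Table 1 grades neo-epithelialization by wound coverage, but its only stated source, a 2 mm wound-edge punch, cannot establish grades 2 and 3 except in long, narrow wounds

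*Combined protocol and SAP*

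**What the plan says.** The histology paragraph under Outcome Measures specifies "punch biopsies (2 mm) from the wound edge at baseline and day 5 post-intervention" and lists "neo-epithelialization (0-3 scale") among the parameters assessed. Data Collection and Measurement repeats that the histological evaluation used wound biopsies and names no other source.

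In Table 1 the measurement column for this parameter reads "Measured as epithelial migration distance from wound edge". The criteria column is on a different scale:

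- grade 0: "No epithelial migration"
- grade 1: "Minimal migration (<25% wound coverage")
- grade 2: 25–75% coverage
- grade 3: more than 75% coverage

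No rule converts a distance into a coverage, and no denominator for coverage is given. The title of Table 1 also names a different site: "Histological parameters evaluated in the ulcer bed at baseline and on day five of application". The eligibility paragraph of Materials and Methods admits wounds larger than 20 cm² and smaller than 75 cm².

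**The concern.** The measurement column and the grades describe different quantities. A distance can be read from an edge specimen. The share of a whole wound that is covered cannot, unless the wound is so narrow that 2 mm is a sizeable part of it. A pathologist who follows the table then has two choices: use only the bottom of the scale, or judge coverage from something outside the slide that the plan does not describe. The first compresses any difference between arms, and the second cannot be reproduced. Blinding of the pathologists, stated under Randomization and Blinding, protects against allocation bias but does not supply the missing denominator.

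This is the histology parameter that bears most directly on epithelialization, which the Introduction names as something NPWT alone may not achieve rapidly. The site wording adds to the problem, because a sample from the bed has no edge from which to measure a distance.

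**Working it through.** The plan gives no figure for this point, so there is nothing to reproduce. The check is geometric.

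**Inputs.** Wound area A is above 20 and below 75 cm² (eligibility paragraph). The punch is 2 mm, from the wound edge (Outcome Measures). The cuts are 25% and 75% (Table 1). Wound shape is not given, so it is an assumption and is varied below.

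**Case most favourable to the scale.** The full 2 mm of the punch lies inside the wound, it is completely epithelialized, and the same advance d holds around the entire margin.

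**Circle.** With r = √(A/π):

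- coverage = 1 − (1 − d/r)²
- advance needed for 25% = r(1 − √0.75)
- advance needed for 75% = r/2

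| A (cm²) | r (mm) | Coverage, d = 2 mm | Coverage, d = 1 mm (punch straddles the edge) | Advance for 25% (mm) | Advance for 75% (mm) |
|---|---|---|---|---|---|
| 20 | 25.2 | 15.2% | 7.8% | 3.4 | 12.6 |
| 47.5 | 38.9 | 10.0% | 5.1% | 5.2 | 19.4 |
| 75 | 48.9 | 8.0% | 4.1% | 6.5 | 24.4 |

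For a 2 mm rim to reach 25%, the radius would have to be at most 0.2/(1 − √0.75) = 1.49 cm. That is an area of 7.0 cm², well below the entry minimum.

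**Rectangle.** With width w and length L in cm, coverage = 1 − (w − 0.4)(L − 0.4)/A.

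- Square: 17.1% at 20 cm² and 9.0% at 75 cm².
- 3:1: 19.9% and 10.5%.
- 25% is first reached at about 1.8 × 11.1 cm for 20 cm² (about 6:1). Check: 1 − (1.4 × 10.7)/20 = 25.1%.
- At 30 cm² it takes about 1.7 × 17.4 cm (10:1), and at 75 cm² about 1.6 × 45.6 cm (28:1).
- 75% needs a width of about 0.5 cm, or 70:1 even at 20 cm².

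**Ellipse.** Coverage = (P·d − π·d²)/A, where P is the perimeter. At 20 cm² this reaches 25% at about 6:1, as for the rectangle. Irregular outlines, which also lengthen the margin, were not modelled.

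**Censoring.** If the epithelial tongue ends inside the punch, its length is observed, and in the shapes above other than the narrow ones the result is grade 1. If the punch is covered from side to side, the advance is known only to be at least 2 mm (at least 1 mm if the punch straddles the edge). That finding is compatible with grades 1, 2 and 3.

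**The case against.** **Coverage may mean percent of the section.** Only grade 1 says wound coverage; grades 2 and 3 say coverage alone, and the parameter is read on biopsies. If the denominator were the wound surface visible on a 2 mm section, the cuts would fall at 0.25 × 2 = 0.5 mm and 0.75 × 2 = 1.5 mm, and all four grades could be reached. This is the strongest rebuttal. It does not settle the matter: the documents nowhere say so, the grade 1 wording points the other way, and the cuts would shift with how much of each punch lies inside the margin. The denominator would still have to be stated.

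**The scale may seem to collapse to 0–1 for every specimen.** A reader might infer this, and it is too strong. Wound shape is unknown, post-surgical dehiscence is eligible, and some such wounds may be narrow enough for grade 2. A fully covered punch is also censored; it does not show coverage below 25%.

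**The parameter is minor.** This stands. The only histology item among the secondary outcomes is vascular infiltration, and Statistical Analysis sets out nothing specific to neo-epithelialization.

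**Length in mm has the same ceiling.** This also stands, and the fix has to allow for it.

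**The site conflict may be only loose wording.** The title heads all six parameters and may be a generic label. The documents describe no separate bed biopsy, so they do not support inferring that two sites were sampled. The wording still needs to be aligned.

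**Conclusion.** The point holds. In eligible circular wounds, a 2 mm advance around the whole margin covers about 15% (at 20 cm²) down to 8% (at 75 cm²), against a cut of 25% for grade 2 and 75% for grade 3. The specimen cannot establish either grade except in long, narrow wounds, from about 6:1 at 20 cm² to 28:1 at 75 cm² for grade 2. Unless coverage means percent of the section, a grader following the text is left with grades 0 and 1, and a fully covered punch cannot be graded with confidence at all.

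The conclusion assumes a regular outline and an even advance around the margin, and takes coverage to mean share of the wound. A reader might go further and doubt the trial's histology or efficacy results in general. The documents do not support that: the primary outcome comes from wound photographs, vascular infiltration is graded by vessel counts per field, and neither they nor the other listed secondary outcomes depend on this scale. The defect is worth correcting but limited to one parameter outside the listed outcomes.

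**What to change.** - **Score.** In Table 1, replace the coverage grades with epithelial tongue length in mm, read blinded on the existing H&E sections. This is the quantity the measurement column already names.
- **Ceiling.** Report fully covered punches as at least the visible length, and record how much of each section lies inside the wound margin. Because of the ceiling, compare arms with a rank-based method; Statistical Analysis already allows the Mann–Whitney test.
- **Status.** Label the result exploratory. The document is dated November 2025 and describes recruitment as having ended in July 2025, so if scoring has been done, label the change post hoc as well.
- **Coverage.** Drop percent coverage as a histology grade. It might seem recoverable from the wound tracings, but the documents describe no area measurement at day 5, and a smaller traced area can also reflect contraction of the margin.
- **Site.** Align the ulcer-bed wording in the Table 1 title with the wound-edge site given under Outcome Measures.

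**Cost.** No new biopsies. Slides already graded must be re-read: up to 104 × 2 = 208 specimens if every patient has both. The documents do not say whether sections were oriented to show tongue length, so some may be unreadable for this purpose. Length remains capped by the 2 mm specimen.
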